11.4 Safety Endpoints

All Adverse Events recorded from the time of enrollment until the subject completes the protocol.

Any AEs reported that are possibly or probably related to the use of the product or related to the procedure within 36 months post last breath test performed or until subject termination will be followed until resolution and if laboratory work is done secondary to AEs and found abnormal, these tests will be followed until normalization or stabilization.

Exalenz Bioscience Ltd.	Last update on: May1, 2016
Study Title: Clinical Study of the BreathID [®] System to train the algorithm for the ¹³ C-Octanoate Breath Test with or without the ¹³ C-Methacetin Breath Test (OBT and MBT respectively) for correlation with histological findings of Non-Alcoholic Fatty Liver Disease (NAFLD)	Protocol No.: NASH-EX-1114
	Version: 1f
Document N^o: CSD00080	Page 32 of 61

11.5 Sample Size estimation

It is estimated that a total of 200 subjects with a fresh and evaluable liver biopsy undergoing OBT and MBT of which at least 50 will be positive for NASH and at least 50 will be positive for NAFLD will enable the estimation of a conservative AUC of 0.75 with a half width of the 95% confidence interval of 0.1.

During the study the correlation between OBT with or without MBT and histological findings of NAFLD will be assessed periodically in order to see if there is any confounding factor(s) affecting the correlation. In the case that such a factor(s) is identified showing a significant difference in correlation, the study population may be increased up to 400 patients.

11.6 Analysis sets

1. Primary analysis set (per protocol): All subjects enrolled in the study with a valid biopsy and valid OBT and MBT results together with the proposed additional biomarkers.
2. Secondary analysis set – ITT: all subjects performing at least one breath test.
3. Safety analysis set: all patients performing at least one breath test

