9 STUDY OBJECTIVES

9.1 Efficacy Objective

The primary objective of the study is to develop an algorithm based on OBT with or without MBT with or without additional clinical and/or laboratory parameters, and its cut-off to correlate with histological findings, as assessed by a central reader, of NAFLD.

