11 STATISTICAL CONSIDERATIONS

11.1 Study Design and Objectives

This is a multicenter, non-randomized, open-label, cross-sectional comparative exploratory study comparing OBT with or without MBT values to histologic findings from liver biopsy associated with NAFLD.

This study will be used to train an algorithm using OBT with or without MBT with or without other commercially available biomarkers and to select a cut-off to determine correlation with histological findings of NALFD and determine clinical outcome at 18 and 36 months, if available.

The modeled algorithm will be validated in a separate study.

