11.2 Primary endpoints

Correlation of histological findings of NAFLD compared to ¹³C-Octanoate Breath Test with or without ¹³C-Methacetin Breath Test with or without additional clinical and/or laboratory parameters.

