11.7.5 Performance Analysis

A model/algorithm will be developed for the correlation between histological findings of NAFLD and OBT with or without MBT. It will be developed using either logistic regression or neural network or any other known methodology. Using a cut-point on the score a binary diagnosis of NASH (Yes/No) or NAFL (Yes/No) will be obtained. The minimal criterion for sufficient efficacy is an Area under the Receiver Operating Characteristics (ROC) Curve (AUC) ≥ 0.75 in this patient population. A potential clinical utility was designated for the algorithm/model output; where this algorithm could aid the clinician in ruling-in or out NASH or NAFL. This will be translated into finding a model prediction cut-point that provides a high sensitivity (true positive rate) and at least moderate specificity (true negative rate), which in turn achieves a high negative predictive value (NPV). High NPV is considered to be near 90% (i.e. 88%) thus sensitivity should be at least 90% and specificity should be at least 50%. Cross validation methods will be used to test algorithm stability.

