11.7.8 Handling of Missing Data

The study variables cannot be evaluated for patients for whom OBT or MBT results or liver biopsy results are not available and therefore these subjects will be left out of the primary efficacy analysis. Demographic clinical characteristics and safety data of patients with missing data will be compared to patients with complete data.

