- d. Renal panel and electrolyte panel (BUN, creatinine, electrolytes (Na⁺ and K⁺),
- e. Collection of 4ml of blood for serum and freezing for storage (no preservative tube) where possible.
- f. Hepatic panel (AST, ALT, alkaline phosphatase, GGTP, total bilirubin, direct bilirubin, serum albumin and total protein) - if not available from within 3 months
- g. Additional Coagulation Panel (PTT, fibrinogen) - if not available from within 3 months
- h. Total calcium, PO₄ (phosphate corrected), magnesium - if not available from within 6 months
- i. Lipid profile and HbA1c - if not available within 6 months
- j. Thyroid Panel - if not available within 12 months
- k. Other assays where routinely practiced; (optional): Adiponectin + Leptin + IL6 + CK18, TNF α , C-peptide

NOTE: if possible more than just the essential blood panels (sections a. to d.) will be collected adjacent to the OBT.

7. ¹³C-Octanoate Breath Test:

NOTE: Expected warm-up time for the device to be ready to measure patient's breath is up to 90 minutes. Ensure the device is turned on at least 2 hours prior to scheduled patient visit.

The breath test is performed automatically while the patient is connected to the device using a nasal cannula. The test is of 2 phases: baseline and the sampling phase separated by the administration of the test substrate. The 2 phases' durations are up to 30 and up to 60 minutes respectively.

For more information regarding the OBT procedure please refer to Section 5 of the Investigator's Brochure.

8. Adverse events recording until the subject completes the protocol.

NOTE: Any AEs reported that are possibly or probably related to the use of the product or related to the procedure within 36 months post OBT or until subject termination will be followed until resolution and if laboratory work is done secondary to AEs and

Exalenz Bioscience Ltd.	Last update on: May1, 2016
Study Title: Clinical Study of the BreathID [®] System to train the algorithm for the ¹³ C-Octanoate Breath Test with or without the ¹³ C-Methacetin Breath Test (OBT and MBT respectively) for correlation with histological findings of Non-Alcoholic Fatty Liver Disease (NAFLD)	Protocol No.: NASH-EX-1114
	Version: 1f
Document N^o: CSD00080	Page 39 of 61

found abnormal, these tests will be followed until normalization or stabilization.

9. Diabetic patients will be followed throughout the entire visit and should be instructed to resume their medication immediately after the breath tests.

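### The only primary efficacy set demands valid OBT, MBT and unnamed biomarkers, so patients with a valid biopsy and OBT are dropped even from an OBT-only model that could use them

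*Combined protocol and SAP*

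**What the plan says.** Section 11.6 gives one primary (per-protocol) set for efficacy: "All subjects enrolled in the study with a valid biopsy and valid OBT and MBT results together with the proposed additional biomarkers". The secondary set, labelled ITT, needs only one breath test. It does not require a biopsy, and no analysis is attached to it anywhere in Section 11.

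Section 11.7.8 gives the reason for its missing-data rule: "The study variables cannot be evaluated for patients for whom OBT or MBT results or liver biopsy results are not available". Patients in that position are accordingly excluded from the primary efficacy analysis. The section does not mention biomarkers.

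The aims are wider than that set. Section 9.1 sets out to "develop an algorithm based on OBT with or without MBT with or without additional clinical and/or laboratory parameters". Section 11.1 describes training on "OBT with or without MBT with or without other commercially available biomarkers", and the primary endpoint in Section 11.2 is framed "with or without additional clinical and/or laboratory parameters". Section 11.7.5 plans the model in the same way: "A model/algorithm will be developed for the correlation between histological findings of NAFLD and OBT with or without MBT".

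No section says which markers are the proposed additional biomarkers. Section 12.3 lists the blood panels, and one item is voluntary: "Other assays where routinely practiced; (optional): Adiponectin + Leptin + IL6 + CK18", followed by TNFα and C-peptide.

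**The concern.** The primary set is built for the largest candidate model and then imposed on every smaller one. A patient with an adequate biopsy and a valid OBT, but no MBT, supplies everything an OBT-only algorithm needs. Excluding that patient costs precision. It may also select the sample, because the MBT carries conditions the OBT does not: a medication restriction (Section 10.2, item 6), no smoking that day and no recent paracetamol (Section 10.4), and a further fasting visit within a set window (Section 12.4). Patients who miss it may differ from those who complete it, in a direction that cannot be predicted.

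The biomarker condition adds a second difficulty. Because the markers are not named, membership of the primary set cannot be determined from the plan. If any voluntary assay is among them, Section 11.6 would exclude a patient whose site does not run that assay, even from a model that ignores it.

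**Working it through.** **Which patients each model needs**

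| Candidate model | Inputs needed | What Section 11.6 requires |
|---|---|---|
| OBT only | biopsy, OBT | biopsy, OBT, MBT, biomarkers |
| OBT + MBT | biopsy, OBT, MBT | biopsy, OBT, MBT, biomarkers |
| OBT ± MBT + laboratory markers | as above plus the markers used | biopsy, OBT, MBT, biomarkers |

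The claim in Section 11.7.8 that such patients cannot be evaluated is true of a missing biopsy or a missing OBT. It is true of a missing MBT only when the model uses MBT. The protocol foresees patients without one: exclusion criterion 6 applies only where an MBT is done, Section 12.5 merely presumes that the last breath test is the MBT, and the ITT set accepts a single test.

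**Inputs for the size of the effect**

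- Section 11.5: 200 subjects undergoing both tests, at least 50 with NASH and at least 50 with NAFLD; AUC A = 0.75; 95% half-width 0.1.
- Assumption: 5%, 10% or 20% of patients with biopsy and OBT lack a valid MBT. The documents give no rate.
- Assumption: the positive/negative split is 100/100, 150/50 or 50/150. The case 50/50 uses only half of the 200 and is the least favourable.

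**Formula** (Hanley-McNeil, with n₁ positives and n₀ negatives)

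q₁ = A/(2 − A) = 0.75/1.25 = 0.6

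q₂ = 2A²/(1 + A) = 1.125/1.75 = 0.6429

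variance = [A(1 − A) + (n₁ − 1)(q₁ − A²) + (n₀ − 1)(q₂ − A²)] / (n₁n₀), and half-width = 1.96 × √variance.

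**The plan's own figure.** With A² = 0.5625, q₁ − A² = 0.0375 and q₂ − A² = 0.0804. At 50/50:

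variance = (0.1875 + 49 × 0.0375 + 49 × 0.0804)/2500 = 5.9625/2500 = 0.002385

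SE = 0.0488 and half-width = 0.0957. The Obuchowski binormal variance gives 0.102. Both agree with the stated 0.1.

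**Adding the OBT-only patients back.** Read Section 11.5 as 200 patients who have both tests. The OBT-only model could then use 200/(1 − L) patients: 200/0.95 ≈ 211, 200/0.90 ≈ 222, 200/0.80 = 250. With each class scaled by the same factor, the half-widths are:

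| Split in complete set | Complete set | L = 5% | L = 10% | L = 20% |
|---|---|---|---|---|
| 100/100 | 0.0675 | 0.0658 | 0.0640 | 0.0603 |
| 150/50 | 0.0705 | 0.0687 | 0.0669 | 0.0630 |
| 50/150 | 0.0847 | 0.0825 | 0.0803 | 0.0757 |
| 50/50 (100 patients) | 0.0957 | 0.0933 | 0.0908 | 0.0855 |

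The relative narrowing is about 2.5%, 5% and 11%. The largest absolute change is 0.0957 − 0.0855 = 0.0102.

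**Alternative reading.** The synopsis says at least 200 will be enrolled. If losses come out of 200, a 10% loss gives 0.089 at 50/150 and 0.101 at 50/50. At 50/150 it takes about a 30% loss to reach 0.101.

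**The case against.** The strongest defence is that the plan is coherent about the data it wants. The sample size is stated for patients having both tests, MBT is scheduled for everyone, and its feasibility is considered when the OBT is booked. The phrase about MBT being optional may describe which inputs the final algorithm keeps, not which patients supply data. Choosing between OBT and OBT plus MBT does need a common complete set. The ITT set keeps OBT-only patients, excluded patients will be listed (Section 11.7.3), and their characteristics will be compared with those of complete cases (Section 11.7.8). Section 11.7.8 names only the two tests and the biopsy, so nobody is shown to be lost for want of a biomarker. The study is exploratory, and the algorithm is to be validated separately (Section 8). Finally, one primary set per model could add analytic flexibility.

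Several of these points stand. The common set is right for the comparison, the number lacking only MBT may be small, the biomarker loss is conditional, and the validation study limits the consequences.

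The rest does not remove the problem. Section 11.7.8 justifies exclusion by non-evaluability, not by the need for a paired comparison. The ITT set has no assigned analysis and no biopsy requirement, and listing or describing excluded patients does not use their data. The extra flexibility is contained if each set follows mechanically from the model's inputs and the common set is kept for comparing models.

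**Conclusion.** The concern holds. For an OBT-only algorithm, which the plan expressly allows, the primary set discards evaluable patients for a reason that does not apply to that model. The set also rests on a biomarker list the plan does not contain, and Sections 11.6 and 11.7.8 differ on whether a missing biomarker excludes a patient.

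The effect is limited. Every complete-set Hanley-McNeil half-width above is already below 0.10, and the figure in Section 11.5 is not wrong. The gain rests on assumed rates of missing MBT, on the classes scaling equally, and on 200 being the number with both tests. The direction of any selection effect is unknown. The change should be made because it costs almost nothing, not because the loss is large.

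**What to change.** - In Section 11.6, define the primary set for each candidate model as a valid central biopsy reading plus valid results for the inputs that model uses. For OBT alone that means biopsy and OBT.
- Keep the common complete set, and use it for comparing OBT with OBT plus MBT. AUCs from different model-specific sets are not directly comparable; that is the one real downside.
- Amend Section 11.7.8 so that a missing MBT excludes a patient only from models that use MBT.
- List the proposed additional biomarkers, and state that a missing one excludes a patient only from models that use it.
- Report the number of patients in each set.

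The cost is SAP wording and a little extra programming. No new patients, visits or data are needed.

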11.7 Statistical Analysis

11.7.1 General Considerations

Statistical analyses will be performed using SAS[®] v9.3 or higher (SAS Institute, Cary NC, USA).

If any statistical tests are performed, they will be two-sided. The required significance level of findings will be equal to or lower than 5%. Where confidence limits are appropriate, the confidence level will be 95%.

Baseline values are defined as the last valid value prior to study treatment start.

All statistical analyses of safety and performance measures will be descriptive in nature. Continuous variables will be summarized by a mean, standard deviation, minimum, median and maximum, and categorical variables by a count and percentage. Confidence intervals will be provided where relevant.

If multiple measurements are taken in a single patient, statistics described below will be appropriately modified to accommodate the within patient correlation.

Exalenz Bioscience Ltd.	Last update on: May1, 2016
Study Title: Clinical Study of the BreathID [®] System to train the algorithm for the ¹³ C-Octanoate Breath Test with or without the ¹³ C-Methacetin Breath Test (OBT and MBT respectively) for correlation with histological findings of Non-Alcoholic Fatty Liver Disease (NAFLD)	Protocol No.: NASH-EX-1114
	Version: 1f
Document N^o: CSD00080	Page 33 of 61

11.7.2 Demographic and Other Baseline Characteristics

Demographic, medical and clinical history variables will be tabulated. Continuous variables will be summarized by a mean, standard deviation, minimum, median and maximum, and categorical variables by a count and percentage.

11.7.3 Disposition of Subjects

The numbers of patients who were enrolled will be provided, as well as the reasons for all enrollment discontinuations, grouped by major reason (e.g., lost to follow-up, adverse event, poor compliance). A list of discontinued patients, protocol deviations, and patients excluded from the efficacy analysis will be provided as well

11.7.4 Safety Analysis

The events related to study drug and/or device AEs rate will be presented along with a 95% exact binomial two sided 95% confidence interval. The analysis of all adverse events will include incidence tables and will include analyses by severity, relationship to device or drug and baseline variables.

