9.5 Safety Endpoints

Safety will be assessed by assessing all adverse and serious adverse events occurring in all subjects enrolled from the time of enrollment until the subject completes the protocol.

Any AEs reported that are possibly or probably related to the use of the product or related to the procedure within 36 months post last breath test performed or until subject termination will be followed until resolution and if laboratory work is done secondary to AEs and found abnormal, these tests will be followed until normalization or stabilization.

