1. Eight (8) hours fasting prior to OBT including all PO morning medications except for beta blockers. Diabetic patients that are driving should test their blood sugars to rule out hypoglycemia and respond accordingly.
2. No general anesthesia or sedation within 24 hours prior to OBT
3. No alcohol within 24 hours prior to OBT
4. Patient should be symptom free of any prior intervention (e.g. biopsy)

10.4 On the day of the MBT:

1. Eight (8) hours fasting prior to MBT including all PO morning medications except for beta blockers. Diabetic patients that are driving should test their blood sugars to rule out hypoglycemia and respond accordingly.
2. No smoking on the day of the MBT
3. No paracetamol (acetaminophen) based medications within 24 hours prior to MBT
4. No general anesthesia or sedation within 24 hours prior to MBT
5. No alcohol within 24 hours prior to MBT
6. Patient should be symptom free of any prior intervention (e.g. biopsy)

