12.3 Visit 2: ¹³C-Octanoate Breath Test (OBT)

1. Female patients of childbearing age meeting all criteria will undergo pregnancy test if not available from the past 7 days. Abstinence or oral contraceptives are requested until completion of MBT (second breath test).

Exalenz Bioscience Ltd.	Last update on: May1, 2016
Study Title: Clinical Study of the BreathID [®] System to train the algorithm for the ¹³ C-Octanoate Breath Test with or without the ¹³ C-Methacetin Breath Test (OBT and MBT respectively) for correlation with histological findings of Non-Alcoholic Fatty Liver Disease (NAFLD)	Protocol No.: NASH-EX-1114
	Version: 1f
Document N^o: CSD00080	Page 37 of 61

2. OBT will be performed within 6 months post liver biopsy.
3. Medical History including the following:
 - a. Demographics
 - b. Detailed medical history including liver directed and other concomitant diseases (cardiovascular, respiratory, renal and neurological), presentation, interventions, etiology, habits etc.
 - c. Imaging results,- (if available) Ultrasound, CT and/or MRI, (liver outline, vasculature, evidence of fat etc.), imaging of major hepatic vessels, pancreas, intestines, and liver volume
 - d. Other assays: e.g. HVPG
 - e. Most recent laboratory blood test results within 6 months.
 - f. Concomitant medications
4. Physical examination (targeting liver related findings) including liver related clinical scoring.
5. In preparation for the OBT:
 - a. Eight (8) hours fasting prior to OBT including all PO morning medications except for beta blockers. Diabetic patients that are driving should test their blood sugars to rule out hypoglycemia and respond accordingly.
 - b. No general anesthesia or sedation within 24 hours prior to OBT
 - c. No alcohol within 24 hours prior to OBT
 - d. Patient should be symptom free of any prior intervention (e.g. biopsy)
6. Within one hour prior to the OBT blood will be drawn for the following panels (note the relevant remarks):
 - a. Insulin and Glucose
 - b. Complete Blood count (WBC, Hemoglobin, Platelets) and CRP
 - c. Coagulation: PT (INR)

Exalenz Bioscience Ltd.	Last update on: May1, 2016
Study Title: Clinical Study of the BreathID [®] System to train the algorithm for the ¹³ C-Octanoate Breath Test with or without the ¹³ C-Methacetin Breath Test (OBT and MBT respectively) for correlation with histological findings of Non-Alcoholic Fatty Liver Disease (NAFLD)	Protocol No.: NASH-EX-1114
	Version: 1f
Document N^o: CSD00080	Page 38 of 61

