15 SAFETY CONSIDERATIONS

15.1 Adverse Event Definitions

An adverse event (AE) is any undesirable or unintentional event that occurs during use of the study medical device or drug, whether or not considered related to the investigational product; this includes clinically significant changes in laboratory values related to acetaminophen exposure. As this study is not therapeutic in nature, there will be no therapeutic failures to report. Regardless of severity or relationship to the study investigational product, these are recorded in the patient's CRF, all adverse events occurring during the time period when study investigational product is being administered. Associated with the use of the investigational product is defined as a reasonable possibility that the event may have been caused by the medical device or drug.

NOTE: Any AEs reported that are possibly or probably related to the use of the product or related to the procedure within 36 months post last breath test performed or until subject termination will be recorded and followed until resolution and if laboratory work is done secondary to AEs and found abnormal, these tests will be followed until normalization or stabilization.

Serious Adverse Event (SAE) and Suspected Unexpected Serious Adverse Reactions (SUSAR)

Exalenz Bioscience Ltd.	Last update on: May1, 2016
Study Title: Clinical Study of the BreathID [®] System to train the algorithm for the ¹³ C-Octanoate Breath Test with or without the ¹³ C-Methacetin Breath Test (OBT and MBT respectively) for correlation with histological findings of Non-Alcoholic Fatty Liver Disease (NAFLD)	Protocol No.: NASH-EX-1114
	Version: 1f
Document N^o: CSD00080	Page 44 of 61

A serious adverse event (SAE) is an event that is either:

- a) fatal
- b) life-threatening
- c) results in persistent or significant disability/incapacity
- d) requires or prolongs inpatient hospitalization
- e) is a congenital anomaly or birth defect.

A Suspected Unexpected Serious Adverse Reactions (SUSAR) is an SAE, for which the nature or severity is not consistent with the expected outcomes of the treatment being offered.

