15.2 Relationship to Study medical device

Use the following definitions to assess the relationship between an adverse event and the study medical device.

- Not Related:

Exalenz Bioscience Ltd.	Last update on: May1, 2016
Study Title: Clinical Study of the BreathID [®] System to train the algorithm for the ¹³ C-Octanoate Breath Test with or without the ¹³ C-Methacetin Breath Test (OBT and MBT respectively) for correlation with histological findings of Non-Alcoholic Fatty Liver Disease (NAFLD)	Protocol No.: NASH-EX-1114
	Version: 1f
Document N^o: CSD00080	Page 45 of 61

The event is clearly related to other factors such as the patient's clinical state, therapeutic interventions or concomitant drugs.

- Remotely Related:

The event was most likely produced by other factors such as the patient's clinical state, therapeutic interventions or concomitant drugs and does not follow a known response pattern to the study medical device.

- Possibly Related:

The event has a reasonable temporal relationship to study medical device administration and follows a known response pattern to the study medical device. However, a potential alternate etiology may be responsible for the event. The effect of medical device withdrawal is unclear. Re-challenge information is unclear or lacking.

- Probably Related:

The event follows a reasonable temporal sequence from the time of medical device administration and follows a known response pattern to the study medical device and cannot be reasonably explained by other factors. There is a reasonable response to withdrawal of the medical device. Re-challenge information is not available or advisable.

- Related:

The event follows a temporal sequence from the time of medical device administration and follows a known response pattern to the study medical device and either occurs immediately following study medical device administration, or improves on stopping the medical device, or reappears on repeat exposure.

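### Procedure-related adverse events are a separate class in the safety text, but neither the related-event rate in 11.7.4 nor the relatedness scale in 15.2 has a place for them

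*Combined protocol and SAP*

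**What the plan says.** **Endpoint.** Section 9.5 sets follow-up for "Any AEs reported that are possibly or probably related to the use of the product or related to the procedure within 36 months" after the last breath test. Section 11.4 repeats this, and the note in 15.1 adds that such events are recorded. Procedure is thus a cause in its own right, next to the product.

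**Analysis.** Section 11.7.4 has two parts. The rate: "The events related to study drug and/or device AEs rate will be presented along with a 95% exact binomial two sided 95% confidence interval". The tables: "The analysis of all adverse events will include incidence tables and will include analyses by severity, relationship to device or drug and baseline variables". Neither names the procedure.

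**Grading.** Section 15.2 opens with "Use the following definitions to assess the relationship between an adverse event and the study medical device" and gives five grades. The list of CRF items just before 15.2 likewise asks only for the relationship to the device. No scale is given for the substrate or for the procedure.

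**Procedure.** Sections 10.3 and 10.4 require an 8-hour fast before each test, with oral morning medication other than beta blockers withheld. Both add: "Diabetic patients that are driving should test their blood sugars to rule out hypoglycemia and respond accordingly". Sections 12.3 and 12.4 have diabetic patients followed throughout each visit.

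**Recording window.** Section 11.4 starts at enrollment. Section 15.1 defines an event as "any undesirable or unintentional event that occurs during use of the study medical device or drug" and speaks of recording while the product is being given. Section 12.5 item 2 refers to events after the OBT.

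**The concern.** The fast and the withheld medication are part of the test as patients undergo it, and the protocol ties a specific harm to them. Section 5.1.1 lists diabetes among the major risk factors for NAFLD, and 10.2 excludes only uncontrolled diabetes, so diabetic patients will be enrolled. If the plan is followed as written, the related-event rate describes the device and the substrate and has no place for the preparation that every test requires. A reader of the final report could take a low or zero related-event rate as the risk of the whole test. The tables could not correct that reading, because nothing in the specified data separates a procedure-related event from an unrelated one.

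**Working it through.** The plan states no expected adverse event rate and no precision target for safety, so there is no figure to reproduce. The check is a comparison of sections, followed by an illustration of size.

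**1. Where the procedure category appears**

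| Place | Procedure named? |
|---|---|
| 9.5, 11.4 and note in 15.1 (follow-up) | Yes |
| 15.1, definition of association | No; device or drug |
| CRF items before 15.2 | No; device |
| 15.2, relatedness scale | No; device |
| 11.7.4, rate with interval | No; drug and/or device |
| 11.7.4, tables of all events | No; device or drug |

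The category exists in the endpoint text and is absent from grading and analysis. The substrate also lacks a separate scale, although 11.7.4 plans an analysis by drug.

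**2. How a fasting event would be graded.** In 15.2, the three upper grades all require timing relative to device administration and a known response pattern to the device. The lowest grade reads: "The event is clearly related to other factors such as the patient's clinical state, therapeutic interventions or concomitant drugs". Hypoglycemia from a fast with medication withheld fits that grade, or the next one up, better than any of the upper three. It would then fall outside the rate. This is a prediction about how investigators would use the scale; the documents do not state it.

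**3. Recording window.** An event during the fast before the first test is inside the window of 11.4. Read literally, it is outside the in-use wording of 15.1 and outside the post-OBT wording of 12.5. The safety set in 11.6 requires at least one breath test, so a patient harmed in that fast who never starts a test is also not in the denominator. Before the MBT the case is weaker, since the OBT has already been given.

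**4. Size, as an illustration.** Inputs: N = 200 (11.5) and the exact binomial interval named in 11.7.4. The event counts are assumptions. I also assume one event per patient, no drug- or device-related events, and that none of the procedure-related events enters the planned rate.

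For x events in N, the Clopper-Pearson lower limit is the 0.025 quantile of Beta(x, N − x + 1), and the upper limit is the 0.975 quantile of Beta(x + 1, N − x). For x = 0 the lower limit is 0 and the upper limit is 1 − 0.025^(1/200) = 0.0183.

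| Procedure-related events (assumed) | Planned rate shows | Rate if counted |
|---|---|---|
| 2 | 0% (0 to 1.83%) | 2/200 = 1.0% (0.12 to 3.57%) |
| 3 | 0% (0 to 1.83%) | 3/200 = 1.5% (0.31 to 4.32%) |
| 4 | 0% (0 to 1.83%) | 4/200 = 2.0% (0.55 to 5.04%) |
| 10 | 0% (0 to 1.83%) | 10/200 = 5.0% (2.42 to 9.00%) |

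With 4 or 10 events, the upper limit of the planned interval (1.83%) lies below the point estimate that counting them would give.

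**The case against.** The strongest reply is that nothing is lost. Section 11.7.4 tabulates all adverse events whatever their cause, 11.4 collects from enrollment, 15.4 has all events entered in the case report form, 12.5 adds a safety call at 48 hours, and the note in 15.1 has procedure-related events recorded. This stands against a broader reading, that such harm is missing from the safety analysis: it would be in the tables. It does not answer the narrower point, that the tables cannot show it as procedure-related.

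A reader might infer more in four other places, and the documents do not support it.

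- Hypoglycemia is not the only harm foreseen. Section 15.1 mentions laboratory changes from acetaminophen exposure, and 10.2 excludes patients hypersensitive to the substrates. Hypoglycemia is the harm tied to the fast.
- Harm from the cannula or substrate is not omitted. Section 5.2.4 lists both as components of the system, so the drug and/or device rate covers it.
- It does not follow that a fasting event can never enter the rate. The fast runs on into the test, with up to 30 minutes of baseline and up to 60 of sampling, and an investigator could grade an event in that time as related.
- The planned pre-test blood draw ("Within one hour prior to the OBT blood will be drawn for the following panels") includes glucose, but one value with no pre-fast comparison cannot attribute a low reading to the fast.

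It is also fair that this is an exploratory study to train an algorithm, with descriptive safety analysis, and that 11.7.4 attaches no decision to the rate. That limits the consequence. It does not remove the mismatch between endpoint and analysis.

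**Conclusion.** The point holds in a limited form. The plan recognises procedure-related events as a class, then provides no means to grade, count or display them as such. Events caused by the fast and withheld medication would probably fall outside the only safety rate with an interval, though not outside the tables of all events. The sections on when recording starts contradict each other and must be reconciled.

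The size cannot be derived from the documents, which give neither the share of diabetic patients nor an event rate. The contrast of 0% (0 to 1.8%) with 1.5% (0.3 to 4.3%) shows what three uncounted events in 200 would do; it is not an estimate of what will happen. The correction is worth making because it is cheap and can change a reported safety estimate.

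**What to change.** 1. In 15.1, 15.2 and the CRF, grade relatedness to the test procedure, stated to include the pre-test fast and withheld medication, and to the substrate, alongside the device.
2. In 11.7.4, include procedure-related events in the related-event rate, or give a second rate with its own exact 95% interval. Show the procedure component separately, overall and in diabetic patients.
3. Reconcile the recording windows in 11.4, 12.5 and 15.1 so that events during the pre-test fast are recorded.

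A listing of the pre-OBT glucose values is optional, for the reason given above.

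The cost is additional relatedness grading on the adverse event form, one table and wording in these sections, with no new visits or samples. The downside is a related-event rate that may look slightly less favourable. The change concerns recording and analysis only; it proposes no change to fasting, medication or patient management.
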